9.1.3 Methods for Evaluation of Disease on Pathology

Each biopsy and surgical excision specimen will be reviewed by two pathologists independently to determine the presence of malignancy. If there is a discrepancy, then a third pathologist will be the tie-breaker.

9.2 Other Response Parameters

9.2.1 Methods for Evaluation of Impact on Surgical Management

The treatment plan that would be recommended based on imaging at the time of ADH diagnosis will be documented on a CRF form. This will be compared with the final treatment plan that is created after the CESM study is performed. Included in this evaluation will be a description of additional procedures initiated by the CESM exam. This will include the number of false positive and true positive additional biopsies, additional surgical procedures, and additional department visits.

10. DATA REPORTING / REGULATORY REQUIREMENTS

Adverse event lists, guidelines, and instructions for AE reporting can be found in Section 7.0 (Adverse Events: List and Reporting Requirements).

10.1 Data Reporting

10.1.1 Method

Patients will be registered in the Oncore system. Study patient data will be captured in an institutional RedCap system designed and maintained by the study team.

10.2 Data Safety Monitoring

The DF/HCC Data and Safety Monitoring Committee (DSMC) will review and monitor toxicity and accrual data from this study. The committee is composed of clinical specialists with experience in oncology and who have no direct relationship with the study. Information that raises any questions about participant safety will be addressed with the Overall PI and study team.

The DSMC will review each protocol up to four times a year or more often if required to review toxicity and accrual data. Information to be provided to the committee may include: up-to-date participant accrual; current dose level information; DLT information; all grade 2 or higher unexpected adverse events that have been reported; summary of all deaths occurring within 30 days of intervention for Phase I or II protocols; for gene therapy protocols, summary of all deaths

while being treated and during active follow-up; any response information; audit results, and a summary provided by the study team. Other information (e.g. scans, laboratory values) will be provided upon request.

11. STATISTICAL CONSIDERATIONS

This is a pilot study in which patients with a diagnosis of ADH on percutaneous biopsy will have a CESM prior to surgical excision to determine whether CESM can predict upgrade of atypia to malignancy.

Based on the literature of breast MRI, which we assume to have similar performance to CESM, we would need 130-150 patients to show that the false negative rate is less than 3% with 95% confidence to allow CESM to be used for this indication in clinical practice. Given the limitations of recruiting that number of patients, and the absence of any data on this topic for CESM, a decision was made to do a pilot study to first determine whether CESM can distinguish between benign and malignant pathology.

Therefore:

Null hypothesis: the proportion of patients with positive CESM findings is the same in the malignant and benign groups;

The alternative hypothesis is that the proportion of patients with positive CESM findings is different in the malignant and benign groups (two-tailed hypothesis).

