2.2 Rationale

Preliminary attempts to identify those cases of ADH that will upgrade to cancer using breast MRI has been performed and has shown promise (5-9). CESM is an imaging tool that uses a dual energy technique after contrast administration to identify breast cancer. The exam provides two sets of images for interpretation. One set has the appearance of conventional mammographic images and the other highlights areas of contrast uptake, similar to breast MRI. As a result, a CESM provides information on both morphology/density and vascularity, without the need for breast MRI. This is beneficial as CESM is a lower cost, faster, more universally accessible exam than MRI given that it is an add-on unit to conventional mammography equipment.

Our objective is to perform a preliminary study to determine whether we can predict upgrade of atypia to malignancy using CESM. The results of this study will drive a larger study on the role of CESM in this setting.

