11.2 Sample Size, Accrual Rate and Study Duration

For the primary outcome:

The expected group sizes for 0.05 significance level and 0.9 power, assuming sensitivity of 0.9 and specificity of 0.8 (based on aggregate data from multiple studies in the literature, references 6-10), and 0.2 incidence rate (20% of cases becoming malignant in the sample based on data from our clinical practice), suggest 6 patients in the malignant group, 5.5 of whom are expected to have positive CESM findings, and 24 patients in the benign group, 5 of whom are expected to have positive CESM findings.

Given that we identify 60 number of atypia per year and expect 30% enrollment, we expect recruitment to be approximately 1.5 years.

Although we will be calculating CESM’s performance characteristics (including sensitivity, specificity, positive predictive value, negative predictive value, and false negative rate), we will not be using these performance characteristics as primary objectives in our study as the number of participants involved is too small to draw significant conclusions.

For the secondary outcome: This is exploratory and descriptive statistics will be used to evaluate the impact of CESM on surgical management of ADH.

Accrual Targets					
Ethnic Category	Sex/Gender				
	Females		Males		Total
Hispanic or Latino	5	+		=	
Not Hispanic or Latino	25	+		=	
Ethnic Category: Total of all subjects	30 (A1)	+	(B1)	=	(C1)
Racial Category					
American Indian or Alaskan Native	0	+		=	
Asian	5	+		=	
Black or African American	12	+		=	
Native Hawaiian or other Pacific Islander	0	+		=	
White	13	+		=	
Racial Category: Total of all subjects	(A2)	+	(B2)	=	(C2)
	(A1 = A2)		(B1 = B2)		(C1 = C2)

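### Does the background figure of 130-150 patients for a false negative rate under 3% need correcting because it does not fit the inputs of section 11.2?

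*Combined protocol and SAP*

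**What the plan says.** Section 11 opens by explaining why this is a pilot. It states that "we would need 130-150 patients to show that the false negative rate is less than 3% with 95% confidence", and introduces the figure with "Based on the literature of breast MRI, which we assume to have similar performance to CESM". It then gives two reasons for not running that study: recruiting so many patients is impractical, and no CESM data exist for this use. The pilot's hypothesis follows: whether the proportion with positive CESM differs between malignant and benign excisions.

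Section 11.2 sizes the pilot separately, "assuming sensitivity of 0.9 and specificity of 0.8 (based on aggregate data from multiple studies in the literature, references 6-10", and with "0.2 incidence rate (20% of cases becoming malignant in the sample based on data from our clinical practice". This gives 6 malignant and 24 benign cases, of whom 5.5 and 5 are expected to be CESM-positive. The section also says that the team will calculate "performance characteristics (including sensitivity, specificity, positive predictive value, negative predictive value, and false negative rate", but that these are not primary objectives because the sample is too small.

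On what comes next, section 2.2 says: "The results of this study will drive a larger study on the role of CESM in this setting".

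**The concern.** Section 11 is the only place that says what must be shown for clinical use and how many patients that takes. Its source is breast MRI literature taken to apply to CESM. References 6-10, behind the performance figures in section 11.2, are breast MRI studies by title, so it is natural to read the two calculations together. Read that way, they clash: a test that misses one cancer in ten, in a population with 20% cancers, does not comfortably give a false negative rate under 3% on any usual denominator.

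Two things would be at stake. A pilot that confirmed its assumptions could lead to a follow-on study of 130-150 patients with little chance of success. And because section 11.2 lists a false negative rate without defining it, the pilot's misses could be set against the 3% bar on whichever denominator looked best.

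**Working it through.** **Inputs.** Sensitivity 0.9, specificity 0.8 and upgrade rate 0.2 (section 11.2); bar 3%, confidence 95%, size 130-150 (section 11). The denominator, sidedness and interval method are not stated. The one-sided exact (Clopper-Pearson) limit is used as a favourable reading, with variants noted.

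**Can 130-150 be rebuilt?** With no misses, the smallest n whose upper limit is below 3% is 99 (0/99 gives 2.98%). The CESM-negative share is 0.2 × 0.1 + 0.8 × 0.8 = 0.66, and 99/0.66 = 150. The lower end needs a negative share of 99/130 = 0.76, that is, a specificity of (0.76 - 0.02)/0.8, or about 0.93. So the range could be a zero-miss rule over a span of specificities. This is a reconstruction; the plan does not state it.

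**Rates implied by section 11.2.**
- Per cancer: 1 - 0.9 = 10%.
- Per CESM-negative patient: 0.02/0.66 = 3.03%. From the section's own rounded counts it is 0.5/(0.5 + 19) = 2.56%.
- Per patient: 0.2 × 0.1 = 2%, so 130 × 0.02 = 2.6 to 150 × 0.02 = 3.0 misses expected.

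**Would 130-150 meet the bar at those inputs?**

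| Denominator | Upper limit, no misses (130; 150) | Upper limit, one miss (130; 150) | Chance of meeting the bar (130; 150) |
|---|---|---|---|
| Cancers (26; 30) | 10.9%; 9.5% | 17.0%; 14.9% | none |
| CESM-negatives (about 86; 99) | 3.42%; 2.98% | 5.4%; 4.7% | 0.04%; 2.2% |
| All patients | 2.28%; 1.98% | 3.60%; 3.12% | 7.2%; 4.8% |

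The last row is 0.98^130 = 0.072 and 0.98^150 = 0.048. The interval method matters there: a one-sided Wilson limit tolerates one miss in 150 (2.93%), giving 0.98^150 + 150 × 0.02 × 0.98^149 = 19.6%. At a true rate of 2% per patient, 80% power by the exact test needs 1,542 patients.

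**Does any of this reach the pilot?**
- *Its size.* With 6 malignant and 24 benign cases, 0.9 v 0.2 positive, two-sided Fisher at 0.05, power is 0.920. This agrees with the planned 0.9 and uses neither 130-150 nor 3%.
- *The choice of a pilot.* Section 11.2 expects 60 × 0.30 = 18 patients a year. That is 130/18 = 7.2 to 150/18 = 8.3 years for the larger study. Even the bare minimum of 99 patients takes 99/18 = 5.5 years, and a larger requirement takes longer. The decision stands in every case.
- *Its false negative rate.* One miss is 1/6 = 16.7% per cancer (exact 95% CI 0.4%-64.1%), 1/20 = 5.0% per CESM-negative patient (0.1%-24.9%) or 1/30 = 3.3% per patient (0.1%-17.2%), all above 3%. No misses is 0% on every denominator, with upper limits of 45.9%, 17.6% and 11.6%. At 30 patients the denominator cannot move the estimate across 3%, and no result can show a rate below 3%.

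**The case for a change.** The strongest case for a change is that this is a checkable inconsistency in the plan's only benchmark for clinical use, and that one or two sentences would cure it. If section 11.2 is exactly right, the pilot succeeds about 92% of the time, while a study of 130-150 would meet the bar at most 7% of the time by exact limits. If section 11 rested on a higher sensitivity, the plan holds two unreconciled assumptions, and the chance per patient at 150 is still only 55% at sensitivity 0.98 and 74% at 0.99. Defining the false negative rate beforehand would also prevent a choice after the data are seen.

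The arithmetic stands, and so does the observation that the derivation is missing. Three parts are weaker. Section 11 never says that it used the 0.9, 0.8 and 0.2 of section 11.2, so the contradiction is inferred. The 3.03% against 3% is a knife-edge that the rounded counts in the same section reverse (2.56%), and the ceiling of 7% holds only for the exact limit. Finally, section 2.2 says that the pilot's results, not this background figure, will drive the next study; the harm requires someone to reuse 130-150 unchanged with better data in hand.

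**Conclusion.** The figure of 130-150 cannot be reconciled with the inputs of section 11.2 if those were meant: at 2% missed per patient, the chance of meeting the bar is about 5-7% by the exact limit, and about 20% at 150 by Wilson. It is nonetheless an unexplained background figure, with no role in this trial. No endpoint, test, enrolment target or decision rule uses it or the 3% bar, and annotating or deleting it would change nothing that the pilot does or concludes.

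The undefined false negative rate is a gap that analysts fill sensibly. One minus sensitivity and one minus negative predictive value both follow from measures the plan already commits to calculate, and it already warns that the numbers are too small for firm conclusions.

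This rests on the pilot staying near 30 patients and on the follow-on study being sized from the pilot's results, as section 2.2 indicates. Whoever designs that study should start from those results and not carry 130-150 forward.

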11.1 Study Design/Endpoints

The primary outcome will be whether the biopsy site on CESM is coded as benign or malignant and how that correlates with the pathologic diagnosis of the surgically excised specimen, as benign or malignant.

The biopsy site and up to 2 additional findings will be coded according to the Breast Imaging-Reporting and Data System (BI-RADS), ranging from 1-5. An overall code for each exam will then be generated that corresponds to the most suspicious finding in the study. BI-RADS codes 1, 2, and 3 associated with the corresponding categories of negative, benign findings, and probably benign findings will be classified as negative (benign). BI-RADS codes 4 and 5 associated with the corresponding categories of suspicious and highly suspicious for malignancy will be classified as positive (malignant).

Negative truth is defined by a benign diagnosis by the final outcome of pathologic review. Positive truth is defined by a malignant diagnosis (ductal carcinoma in situ and invasive cancer) by the final outcome of pathologic review.

The secondary outcome will be to understand the impact of CESM for ADH evaluation on surgical management. The pre-CESM and post-CESM final surgical management plans will be compared descriptively.

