Pathology: Two pathologists will review the percutaneous biopsy specimen and the excisional biopsy specimen and provide independent interpretations regarding the presence/absence of

ADH, DCIS, and invasive cancer. If there is disagreement, a third pathology will be the tie-breaker. Final pathology will be recorded on the case report form as well as the online medical record.

Surgical Management: The presumed initial surgical treatment plan will be recorded based on the imaging findings at the time of diagnostic imaging. The final surgical treatment will also be recorded.

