1.2 Primary Objectives

To determine whether CESM can predict upgrade rates of biopsy proven ADH at surgical excision

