3.2 Exclusion Criteria

- 3.2.1 Participants with a core biopsy diagnosis of atypia with associated malignancy (in the same quadrant) will be excluded.
- 3.2.2 Participant had a breast MRI that was performed after the diagnosis of ADH but before surgical excision
- 3.2.3 Participants who have a known allergy to contrast media.
- 3.2.4 Participants who have a known severe allergic response to one or more allergens, as defined by anaphylaxis.
- 3.2.5 Participants with persistent asthma as defined by the National Heart, Lung, and Blood Institute.
- 3.2.6 Participants with renal insufficiency or failure, as determined by a point of care renal function blood test.
- 3.2.7 Participants who are breastfeeding are excluded because there is an unknown but potential risk for adverse events in nursing infants secondary to contrast administration in the mother.
- 3.2.8 Participants with the following underlying medical conditions: multiple myeloma, myasthenia gravis, dysproteinemias, severe cardiac disease, aortic stenosis, primary pulmonary hypertension, cardiac arrhythmia, or severe cardiomyopathy. These underlying medical conditions may make the participant more likely to develop a contrast reaction. This is based on the ACR contrast manual version 10.3 and hospital policy.
- 3.2.9 Participants with thyroid carcinoma or thyroid disease for whom systemic radioactive iodine therapy is part of planned diagnostic work-up or treatment within 2 months following the contrast mammogram study.
- 3.2.10 Participants with a concurrent active illness including, but not limited to, symptomatic congestive heart failure, unstable angina pectoris, cardiac arrhythmia, thyroid storm.
- 3.2.11 Pregnant women are excluded from this study because CESM uses radiation with the potential for teratogenic or abortifacient effects. This will be defined by a urine pregnancy test prior to the CESM study.

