4. REGISTRATION

4.1 General Guidelines for DF/HCC Institutions

Institutions will register eligible participants in the Clinical Trials Management System (CTMS) OnCore. Registrations must occur prior to the initiation of protocol therapy. Any participant not registered to the protocol before protocol therapy begins will be considered ineligible and registration will be denied.

An investigator will confirm eligibility criteria and a member of the study team will complete the protocol-specific eligibility checklist.

Following registration, participants may begin protocol therapy. Issues that would cause treatment delays should be discussed with the Overall Principal Investigator (PI). If a participant does not receive protocol therapy following registration, the participant's registration on the study must be canceled. Registration cancellations must be made in OnCore as soon as possible.

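### Does the plan need a rule for participants whose core biopsy is re-read as malignant, so that they are not counted as ADH upgrades?

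*Combined protocol and SAP*

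**What the plan says.** The primary objective (1.2) is "To determine whether CESM can predict upgrade rates of biopsy proven ADH at surgical excision". The primary outcome (11.1) takes the CESM coding of the biopsy site and asks "how that correlates with the pathologic diagnosis of the surgically excised specimen, as benign or malignant". The same section then defines truth: "Positive truth is defined by a malignant diagnosis (ductal carcinoma in situ and invasive cancer) by the final outcome of pathologic review".

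Both specimens are reviewed. Section 1.1 states "Two pathologists will review the percutaneous biopsy specimen and the excisional biopsy specimen and provide independent interpretations" for ADH, DCIS and invasive cancer, and adds "If there is disagreement, a third pathology will be the tie-breaker". Section 9.1.3 repeats this: "Each biopsy and surgical excision specimen will be reviewed by two pathologists independently to determine the presence of malignancy". Section 1.1 also has the final pathology entered on the case report form.

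On entry, 3.2.1 reads "Participants with a core biopsy diagnosis of atypia with associated malignancy (in the same quadrant) will be excluded". Section 4.1 places the check at registration: "An investigator will confirm eligibility criteria and a member of the study team will complete the protocol-specific eligibility checklist". The three off-study reasons in 5.3 (no excision within 2 years, withdrawal of consent, death) do not include a changed core read. Section 11.4 only points back to 11.1 and 11.2, and neither defines an analysis set.

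**The concern.** A second read of the core for DCIS and invasive cancer can return a diagnosis different from the one on which the participant was enrolled. The plan gives no instruction for that event.

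Two readings are open:

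- **Out.** Read with the consensus core, 3.2.1 excludes her, and 1.2 concerns only ADH proven on biopsy.
- **In.** Eligibility was settled at registration, 5.3 does not remove her, and 11.1 takes truth from the excision. If the excision shows cancer, she joins the malignant group.

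On the second reading a cancer that was in the core all along is called an upgrade, although nothing was left to predict. Only 6 malignant cases are planned, so one participant is a sixth of that group. If the choice were made after CESM reads had been set against excision pathology, it could be made with the answer in view.

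**Working it through.** **Inputs.** From 11.2: significance level 0.05, power 0.9, sensitivity 0.9, specificity 0.8 (so 0.2 positive among benign), and 6 malignant and 24 benign cases. From section 11: a two-tailed hypothesis. Assumed, because the documents do not say: Fisher's exact test; exactly one core-malignant case, placed among the 6; and her chance s of a positive CESM read at the site, taken as 0.2, 0.5 or 0.9.

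**Formula.** Power = Σ over (a, b) of P(a)·P(b)·1[Fisher p ≤ 0.05]. Here a is the number CESM-positive among the malignant and b ~ Bin(24, 0.2).

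**The plan's own figure.** With a ~ Bin(6, 0.9), power is 0.920, in line with the stated 0.9.

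**One such case, true upgrades detected at 0.9.** If she is counted, a is Bin(5, 0.9) plus one draw at s. If she is left out, a ~ Bin(5, 0.9) with 24 benign.

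| s | Power, counted | Power, left out | Verdicts differ |
|---|---|---|---|
| 0.2 | 0.797 | 0.875 | 10.4% |
| 0.5 | 0.849 | 0.875 | 8.8% |
| 0.9 | 0.920 | 0.875 | 6.7% |

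**One such case, CESM unable to detect true upgrades (0.2 in both groups).** The chance of a significant result, counting her, is 0.022, 0.038 and 0.060 for s = 0.2, 0.5 and 0.9. Leaving her out it is 0.020. The nominal 0.05 is passed only at the highest assumed s.

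**Single results near the plan.** The plan expects about 5.5 of 6 and 5 of 24 positive.

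- 5/6 v 5/24: p = 0.009.
- A CESM-positive case leaves, 4/5 v 5/24: p = 0.022.
- The CESM-negative case leaves, 5/5 v 5/24: p = C(10,5)/C(29,5) = 252/118,755 = 0.002.

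All three are significant.

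**Single results at the boundary.** 4/6 v 5/24 (p = 0.049) becomes 3/5 v 5/24 (p = 0.112) when a positive-read case leaves. 4/6 v 6/24 (p = 0.141) becomes 4/5 v 6/24 (p = 0.036) when a negative-read case leaves. The verdict can turn in either direction, so neither choice always favours the hypothesis.

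**Against ordinary variation.** The group sizes are not fixed. With the malignant count M ~ Bin(30, 0.2), P(M ≤ 5) = 0.43, and Fisher power averaged over M is 0.873. Chance in the case mix alone therefore brings power to about the level reached by leaving one case out (0.875).

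**The passages side by side.** Section 5.3 governs leaving the study, not membership of an analysis set, so its silence is not a rule that she stays in. Neither 1.1 nor 9.1.3 dates the core review relative to registration. If the review comes first, 3.2.1 applies directly and the question does not arise. A cancer seen only in the core, with a benign excision, is negative truth under the outcome sentence of 11.1, because that sentence names the excised specimen.

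**The case for a change.** The strongest case for a change is that the plan provides for a core re-read and then says nothing about its result. Neither 3.2.1 nor 1.2 states which read counts, or whether exclusion can act after enrolment. A core re-read as neither ADH nor cancer has no rule either. Pilot status is only a partial answer, since the trial tests a two-tailed hypothesis with stated power and is meant to lead to a larger study (2.2). A sentence in 11.1 would cost almost nothing and need no new data.

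Most of that is true as description: the rule is unwritten, and a boundary result could turn on it. Two affected CESM-positive cases would also matter even at the planned result, since 3/4 v 5/24 gives p = 0.058.

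What does not follow is that the plan is wrong. Either set can be defended, and the objection does not show that one of them is right. Section 11 narrows the pilot to telling benign from malignant pathology, and for that hypothesis a cancer confirmed at excision is a proper malignant case whatever the core shows. What suffers is the word upgrade in 1.2. The size of the problem also rests on a number of reclassified cores that the documents never give.

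**Conclusion.** No change follows. This is a detail that the plan leaves to the analyst, and its other provisions are enough to settle it. The consensus core read is recorded, 3.2.1 and 1.2 show which participants the study is about, and 11.1 ties the outcome to the excised specimen. If a core read does change, a competent report would give the number of such cases and the result with and without them, and the data for both will exist.

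The effect is modest and conditional. One assumed case among the 6 lowers power from 0.92 to 0.875 if she is left out, or to between 0.80 and 0.92 if she is counted. The two sets disagree in about 7% to 10% of trials that contain such a case, which is not a risk for the trial as a whole. The chance of a false positive result rises above 0.05 only at s = 0.9, where it is 0.060. At the planned result one case leaves the verdict unchanged. These figures assume Fisher's exact test and exactly one reclassified case. With two or more the effect would be larger, and nothing in the documents says how likely that is.
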